13.3 General Statistical Analysis

Patient demographics, AEs and SAEs, disease status, treatment dosing level, treatment status, clinical response, time-to-event intervals etc. will be recorded and summary descriptive statistics will be calculated. The clinical response rates will also be summarized using descriptive statistics for each cohort, along with their corresponding 95% confidence intervals.

13.4 Analysis of Primary Endpoints

The primary endpoint is whether a patient has a 6-month PFS or not. The proportion of response-evaluable patients who have 6-month PFS in the entire cohort and in PDGFR α expressing tumor and their confidence intervals will be calculated, respectively. The Kaplan-Meier method will be used to describe the time to progression and the median time to progression will be estimated, along with its 95% confidence intervals ([40](#)), for the entire population and for PDGFR α expression, respectively. Cox regression analysis will be used to evaluate baseline characteristics and any potential covariates.

13.5 Analysis of Secondary Endpoints

The overall best response rate to the drug combination will be estimated for the entire study population and for the PDGFR α -expressing high-grade glioma cohort, along with the 95% confidence intervals.

The Kaplan-Meier method will be used to describe the time to overall survival and the median time to overall survival will be estimated, and along with its 95% confidence intervals, for the entire population and for PDGFR α expression, respectively. Cox regression analysis will be used to evaluate baseline characteristics and any potential covariates.

13.6 Safety Lead-in, and Safety Stopping Rule

13.6.1 Safety Lead-in

The first 6 patients will be treated as a single dose-level safety lead-in prior to continuation of accrual of the entire study cohort. The lead-in rule is designed for a “3+3” study and is used to enhance safety analysis for the first 6 patients on the study, wherein the sequential stopping rule has considered the variability of toxicity rate by confidence intervals based on observed data and scenarios where unacceptable toxicity could occur prior to study suspension. Patients will be evaluated for qualifying toxicities as defined in Section [6.4.2](#). If < 2 of 6 qualifying toxicity-evaluable patients complete the first 4 weeks of therapy without a qualifying toxicity, then the dose is considered safe for expansion to the remainder of the entire study cohort. If ≥ 2 of 6 qualifying toxicity-evaluable patients experience a qualifying toxicity during the first 4 weeks of therapy, doses will be modified and an additional 6 patients enrolled for qualifying toxicity evaluation. In this case, the protocol will be placed on hold until the protocol is amended to specify the modified doses. Once a dose has been identified wherein < 2 of 6 patients develop a qualifying toxicity during the first 4 weeks of therapy, then that dose will be used for enrollment of the entire study cohort. In the event that toxicity develops late, the stopping rule below will remain in effect to trigger review by the DSMC.

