13 STATISTICAL CONSIDERATIONS

13.1 Study Design

This is a single-arm phase 2 study of sorafenib, valproic acid, and sildenafil in the treatment of patients with recurrent high-grade glioma. The primary objective is to determine the efficacy of the drug combination in terms of 6-month PFS. This study will be conducted through an adaptive design potentially including 2 Simon's two-stage mini-max designs. Initially, recurrent high-grade glioma patients will be enrolled, regardless of tumor molecular subtype, to determine the efficacy of the drug combination. If efficacy criteria are not met in patients inclusive of all molecular subtypes, then only patients with tumors that express PDGFR α will be enrolled. Therefore, 2 Simon's designs may be included; the first is for patients in the entire cohort and the second is for patients with PDGFR α expressing tumors only if efficacy criteria are not met in the entire cohort. Details on the rationale of the adaptive design can be found in Section [1.9](#).

The total expected sample size is estimated to be 44, with a range from 32 to 66 patients.

Both a safety lead-in and a safety stopping rule are provided to monitor whether there are "too many" unexpected toxicities related to the drug combination, as patients continue being enrolled in the study. To ensure safety with respect to any interaction toxicity effects among the 3 drugs, we provide a safety lead-in rule for the first 6 qualifying toxicity-evaluable patients—like a "3+3" phase 1 design. Once a dose has been identified wherein < 2 of 6 qualifying toxicity-evaluable patients develop a qualifying toxicity during the first 4 weeks of therapy, then that dose will be used for expansion. Qualifying toxicities are defined in Section [6.4.2](#).

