13.6.3 Summary of Safety Monitoring Plan

As mentioned in Section [13.6.1](#), once a dose has been identified wherein < 2 of 6 patients develop a qualifying toxicity during the first 4 weeks of therapy, then the study will be conducted through a Simon's two-stage design (Section [13.1](#)) at that dose for the entire population first and then for the PDGFR α -expressing population. As mentioned in Sections [13.1-13.2](#), 16 patients will be enrolled for the first stage for the entire population. The monitoring plan for the 16 patients is summarized in the table below. Subsequent patients will be monitored as described in Section [13.6.2](#).

Table 16. Summary of Safety Monitoring Plan

Number of qualifying toxicity-evaluable patients	Cumulative safety monitoring plan
The first 6 patients	Must have < 2/6 qualifying toxicity-evaluable patients as indicated by the safety lead-in rule in Section 13.6.1
The next 6 patients	Of the 7-12 qualifying toxicity-evaluable patients, must have < 5-8 patients who develop qualifying toxicities, as indicated in the sequential safety stopping rule in Section 13.6.2
The next 4 patients	Of the 13-16 qualifying toxicity-evaluable patients, must have < 8-10 patients who develop qualifying toxicities, as indicated in the sequential safety stopping rule in Section 13.6.2
Further patients	Continue monitoring of qualifying toxicity-evaluable patients as in Section 13.6.2

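### Section 13.6.1 states the safety lead-in go rule backwards: read literally, the dose is safe to expand when at least 5 of 6 patients have a qualifying toxicity

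*Combined protocol and SAP*

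**What the plan says.** Section 13.6.1 gives the go criterion as follows: "If < 2 of 6 qualifying toxicity-evaluable patients complete the first 4 weeks of therapy without a qualifying toxicity". When that condition is met, the section treats the dose as safe to give to everyone still to be enrolled.

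The next sentence of the same section gives the no-go criterion: "If ≥ 2 of 6 qualifying toxicity-evaluable patients experience a qualifying toxicity during the first 4 weeks of therapy, doses will be modified", with the protocol on hold until it is amended. Later in that paragraph the go condition appears again, with the count the other way round: "Once a dose has been identified wherein < 2 of 6 patients develop a qualifying toxicity during the first 4 weeks of therapy", that dose is used for the whole cohort.

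Two other sections agree with the restatement. Section 13.1 has "Once a dose has been identified wherein < 2 of 6 qualifying toxicity-evaluable patients develop a qualifying toxicity during the first 4 weeks of therapy", and the opening text of Section 13.6.3 has "once a dose has been identified wherein < 2 of 6 patients develop a qualifying toxicity".

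The first row of Table 16 (Section 13.6.3) reads "Must have < 2/6 qualifying toxicity-evaluable patients as indicated by the safety lead-in rule" and points back to Section 13.6.1. It does not say what those patients must have experienced. The next two rows do name the event.

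**The concern.** The go sentence counts patients who finish four weeks free of a qualifying toxicity and accepts the dose when that count is 0 or 1. A lead-in with no toxicity in any of the six patients therefore fails to qualify as safe, while one with toxicity in all six does qualify. Every other complete statement of the threshold counts patients who have a toxicity.

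The rule guards the step from six patients to the full cohort. Section 13.1 says the lead-in is there to protect against interaction toxicity among the three drugs. Sections 1.2 and 1.4 report no earlier high-grade glioma study of sorafenib with an HDAC inhibitor, and no CNS tumour study of sorafenib with an efflux-pump modulator such as sildenafil. No other numerical rule covers the first six patients, since the boundaries in Section 13.6.2 start at 5 of 7. Whoever applies or audits the gate from Section 13.6.1 has to decide which of two adjacent sentences to disregard.

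**Working it through.** **Inputs**
- Literal go rule, Section 13.6.1, first decision sentence: safe if fewer than 2 of 6 complete four weeks free of a qualifying toxicity.
- Hold rule, Section 13.6.1, next sentence: modify doses and hold if 2 or more of 6 have a qualifying toxicity.
- Go rule as stated later in 13.6.1, in 13.1 and in 13.6.3: expand if fewer than 2 of 6 have a qualifying toxicity.
- Lead-in evaluability, Section 10.1: a patient counts only after completing cycle 1 or having a qualifying toxicity before it ends; others are replaced.

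The plan gives no operating characteristic for the lead-in, so there is no stated figure to reproduce.

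**Step 1: put the rules on one count.** Let X be the number of the 6 evaluable patients with a qualifying toxicity. Under Section 10.1, an evaluable patient who does not finish cycle 1 free of toxicity has had one, so the number free of toxicity is 6 − X.
- Literal go rule: 6 − X < 2, that is X ≥ 5.
- Hold rule: X ≥ 2.
- Go rule elsewhere: X ≤ 1.

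**Step 2: run through every possible result.**

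| X | Free of toxicity | Literal sentence | Next sentence | Statements elsewhere |
|---|---|---|---|---|
| 0 | 6 | not called safe | no hold | expand |
| 1 | 5 | not called safe | no hold | expand |
| 2 | 4 | not called safe | hold | do not expand |
| 3 | 3 | not called safe | hold | do not expand |
| 4 | 2 | not called safe | hold | do not expand |
| 5 | 1 | safe | hold | do not expand |
| 6 | 0 | safe | hold | do not expand |

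The literal sentence and the statements elsewhere agree only for X = 2, 3 or 4. At X = 5 or 6, two consecutive sentences order opposite actions.

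**Step 3: size of the difference.** Take X as binomial with 6 patients and true toxicity rate p.
- Literal: P(X ≥ 5) = 6p⁵(1 − p) + p⁶.
- Elsewhere: P(X ≤ 1) = (1 − p)⁶ + 6p(1 − p)⁵.

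At p = 0.10:
- literal: 6 × 0.00001 × 0.9 + 0.000001 = 0.000055
- elsewhere: 0.531441 + 0.354294 = 0.8857

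At p = 0.70:
- literal: 6 × 0.16807 × 0.3 + 0.117649 = 0.4202
- elsewhere: 0.000729 + 0.010206 = 0.0109

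| True rate p | Literal: P(safe) | Elsewhere: P(expand) |
|---|---|---|
| 0.10 | 0.0001 | 0.8857 |
| 0.20 | 0.0016 | 0.6554 |
| 0.35 | 0.0223 | 0.3191 |
| 0.50 | 0.1094 | 0.1094 |
| 0.60 | 0.2333 | 0.0410 |
| 0.70 | 0.4202 | 0.0109 |
| 0.80 | 0.6554 | 0.0016 |

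The literal probability of a safe call rises with toxicity. It is the mirror image of the other rule, and the two cross at 50%. Of these rates only 35% comes from the plan (the acceptable grade 3 or higher rate in Section 13.6.2); the others are illustrative.

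**The case against.** The strongest reply is that the plan corrects itself. The next sentence, the later restatement in the same paragraph, Section 13.1 and the text directly above Table 16 all count patients with toxicity, and that last text presents its version as what Section 13.6.1 says. The later rows of Table 16 also name the event. This stands as far as intent goes: fewer than 2 of 6 with a toxicity is clearly what was meant, and an investigator would probably apply it.

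A second reply is that harm is limited. At 5 or 6 toxicities the next sentence already requires a hold. Each qualifying toxicity goes to the DSMC within 2 business days (Section 8.6), and the study team reviews further enrolment at documented meetings (Section 14.1). If expansion did go ahead, the cumulative boundary of 5 of 7 would stop accrual at the seventh evaluable patient. These safeguards lower the chance of harm, but the last acts only after another patient has been treated, and none of them removes the contradiction.

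Third, at 0 or 1 toxicities the faulty sentence is merely not triggered. It does not call the dose unsafe, and the later sentence then permits expansion. That is right: the outright contradiction is confined to 5 or 6 toxicities, and at 0 or 1 the go sentence fails to give the go it should give.

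Finally, the probabilities assume that the sentence is applied alone, at rates that are mostly not the plan's. They describe the literal reading and do not forecast how the trial would be run. At 35% the literal rule would call the dose safe only 2.2% of the time.

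**Conclusion.** The concern holds. The operative go sentence in Section 13.6.1 is inverted and conflicts with the sentence after it, with its own restatement and with Sections 13.1 and 13.6.3. It differs from those statements at 0, 1, 5 and 6 toxicities out of 6. Read literally, it gives a safe call with probability 0.0055% rather than 88.6% at a true rate of 10%, and 42.0% rather than 1.1% at 70%. These figures rest on six independent patients with a common toxicity rate, the Section 10.1 evaluability definition, and the sentence being applied as written.

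The intended design is coherent and is not in question. This is an internal inconsistency in wording, and the surrounding text makes a wrong decision unlikely. It must still be fixed, because it is the go criterion for exposing the full cohort and the table meant to summarise it refers back to the faulty section.

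**What to change.** In Section 13.6.1, rewrite the go sentence to count toxicities: the dose is safe for expansion if fewer than 2 of the 6 lead-in evaluable patients have a qualifying toxicity in the first cycle (equivalently, if at least 5 of the 6 finish it free of one). In the first row of Table 16, name the event, so that the cell requires fewer than 2 of 6 evaluable patients with a qualifying toxicity. Sections 13.1 and 13.6.3 and the hold sentence can stay as they are.

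The cost is one sentence and one table cell in a protocol amendment. Sample size, thresholds, visits and analyses do not change.

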13.6.2 Sequential Safety Stopping Rule after the Safety Lead-in

In addition to the safety lead-in described above, a formal sequential stopping guideline, which is based on the occurrence rate of qualifying toxicities, is designed for a phase 2 study, with a relatively looser threshold than the safety lead-in rule. If the stopping guideline is reached, accrual is stopped and a thorough review of the safety data is completed by the DSMC. The stopping guideline indicates a level of concern based on the occurrence rate of qualifying toxicities. However, the stopping guideline is not an indicator that an insurmountable safety problem exists. Likewise, the fact that a stopping guideline is not reached does not provide assurance that the drug combination is safe. Qualifying toxicity is defined in Section [6.4.2](#).

Previous studies of sorafenib have shown the acceptable occurrence rate for grade 3 or greater toxicities is $\leq 35\%$ ([41](#)). Using a binomial probability calculation, values of “m” (number of patients with qualifying toxicities) and “n” (number of qualifying toxicity-evaluable patients that have been treated) are selected such that the two-sided 95% confidence interval of the sequential observed occurrence toxicity rate keeps containing the prefixed acceptable occurrence rate $\leq 35\%$.

More specifically, the following values of m/n apply to those patients who are qualifying toxicity evaluable: 5/7, 6/8-9, 7/10-11, 8/12-13, 9/14-15, 10/16-17, 11/18-19, 12/20-21, 13/22-23, 14/24-25, 15/26-28, 16/29-30, 17/31-32, 18/33-34, 19/35-37, 20/38-39, 21/40-41, 22/42-44, 23/45-46, 24/47-48, 25/49-51, 26/52-53, 27/54-56, 28/57-58, 29/59-61, 30/62-63, 31/64-65, 32/66. If, at any time, m/n reaches the values shown, accrual to the study protocol is stopped and the accumulated safety data is submitted to the DSMC for evaluation. Please refer to Section [6.4.2](#) for a list of qualifying toxicities.

13.6.3 Summary of Safety Monitoring Plan

As mentioned in Section [13.6.1](#), once a dose has been identified wherein < 2 of 6 patients develop a qualifying toxicity during the first 4 weeks of therapy, then the study will be conducted through a Simon's two-stage design (Section [13.1](#)) at that dose for the entire population first and then for the PDGFR α -expressing population. As mentioned in Sections [13.1-13.2](#), 16 patients will be enrolled for the first stage for the entire population. The monitoring plan for the 16 patients is summarized in the table below. Subsequent patients will be monitored as described in Section [13.6.2](#).

Table 16. Summary of Safety Monitoring Plan

Number of qualifying toxicity-evaluable patients	Cumulative safety monitoring plan
The first 6 patients	Must have < 2/6 qualifying toxicity-evaluable patients as indicated by the safety lead-in rule in Section 13.6.1
The next 6 patients	Of the 7-12 qualifying toxicity-evaluable patients, must have < 5-8 patients who develop qualifying toxicities, as indicated in the sequential safety stopping rule in Section 13.6.2
The next 4 patients	Of the 13-16 qualifying toxicity-evaluable patients, must have < 8-10 patients who develop qualifying toxicities, as indicated in the sequential safety stopping rule in Section 13.6.2
Further patients	Continue monitoring of qualifying toxicity-evaluable patients as in Section 13.6.2

13.7 Evaluability for Qualifying Toxicity, Toxicity, Response

Each registered patient will be deemed as evaluable for toxicity, qualifying toxicities and response as per Section [10.1](#):

For response evaluability, the patients are coded as having a response or not.

- Responders - Best response assessment is complete response or partial response
- Non-Responders - Best response assessment is stable disease or progressive disease or those patients who were not assessed or not evaluable
- The coding of patients as responders or non-responders will be made by the study team with the concurrence of the biostatistician.

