3.3 Secondary Endpoints

- 3.3.1 Proportion of patients evaluable for response, with tumors that express PDGFR α , with 6-month PFS defined as the time from the first day a patient receives study treatment until time of progression per RANO or Macdonald criteria or death, whichever occurs first.
- 3.3.2 Overall response rate (CR+PR), using RANO or Macdonald criteria, in patients evaluable for response regardless of tumor PDGFR status

- 3.3.3 Overall response rate (CR+PR), using RANO or Macdonald criteria, in patients who are evaluable for response and who have tumors that express PDGFR α .
- 3.3.4 Proportion of patients evaluable for response, regardless of tumor PDGFR status, who are alive at 12 months after the first day a patient receives study treatment. OS defined as the time from the first day a patient receives study treatment until death by any cause.
- 3.3.5 Proportion of patients evaluable for response with tumors that express PDGFR α who are alive at 12 months after the first day a patient receives study treatment. OS defined as the time from the first day a patient receives study treatment until death by any cause.
- 3.3.6 AEs using NCI Common Terminology Criteria for Adverse Events, Version 4.0 (CTCAE v4.0).

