10 MEASUREMENT OF EFFECT

10.1 Definitions

Evaluable for toxicity. All patients will be evaluable for toxicity from the time of their first treatment with sorafenib and/or valproic acid and/or sildenafil.

Evaluable for qualifying toxicities for the safety lead-in. Only those patients who have completed the first cycle of therapy (or have experienced a qualifying toxicity prior to the end of the first cycle) will be evaluable for the safety lead-in. Qualifying toxicities will be defined in the first cycle only. Patients must have completed twice-daily sorafenib dosing for at least 21 out of the first 28 days to be considered to have had sufficient exposure to the regimen for qualifying toxicity evaluation. Patients who are not evaluable for the qualifying toxicity assessment for the safety lead-in will be replaced.

Evaluable for qualifying toxicities for the early stopping rule after the safety lead-in. Patients who have initiated the first cycle of therapy will be considered evaluable for the early stopping rule. Qualifying toxicities will be defined in the first cycle only. Patients who are not evaluable for the qualifying toxicity assessment for the early stopping rule will not be replaced unless they were included in the safety-lead in.

Evaluable for objective response. Patients who have been treated with the combination of twice-daily sorafenib and valproic acid for a minimum of 28 days, and have had their disease re-evaluated, will be considered evaluable for response. These patients will have their response classified according to the definitions stated below. Patients who do not complete study dosing for at least 28 days, or those who do not have their disease re-evaluated following initiation of the combination of sorafenib and valproic acid, will be replaced to ensure that a sufficient number of patients will be available for response evaluation.

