13.2 Sample Size/Accrual Rates

The sample size and power are calculated based on Simon's two-stage mini-max design which minimizes the expected maximum sample size ([35](#)). The primary outcome, 6-month PFS, is considered as a binary variable, ie, a patient either has 6-month PFS or not. Per the previous studies of second-line therapy in GBM, we assume that the null hypothesis, the proportion of patients who have 6-month PFS, is $\leq 20\%$, ie, $p_0 \leq 0.2$, which is unacceptably low, and the true proportion is $p_1 = 0.4$. With a one-sided type I error of 5% and power of at least 80%, the first stage will enroll 16 response-evaluable patients. If there are 3 or less response-evaluable patients who have 6-month PFS, then the trial in the unselected patient population will end. If 4 or more response-evaluable patients have 6-month PFS, then the trial will enroll an additional 17 response-evaluable patients into the second stage. If 11 or more out of the total of 33 response-evaluable patients have 6-

month PFS, the drug combination meets efficacy criteria and further studies can be pursued.

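### Section 13.7 counts unassessed patients as non-responders, while 3.3.2, 3.3.3 and 10.1 exclude and replace them, so the response-rate denominator is contradictory

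*Combined protocol and SAP*

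**What the plan says.** The response rate is dealt with in four places in the combined protocol and SAP.

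- **Objectives 2.2.2 and 2.2.3, endpoints 3.3.2 and 3.3.3.** All four confine it to response-evaluable patients. Endpoint 3.3.2 reads: "Overall response rate (CR+PR), using RANO or Macdonald criteria, in patients evaluable for response regardless of tumor PDGFR status". Endpoint 3.3.3 does the same for PDGFRα-expressing tumours.
- **Section 10.1.** Patients given twice-daily sorafenib with valproic acid "for a minimum of 28 days, and have had their disease re-evaluated, will be considered evaluable for response". The group that fails is described as "Patients who do not complete study dosing for at least 28 days, or those who do not have their disease re-evaluated" after starting the combination. These patients "will be replaced to ensure that a sufficient number of patients will be available for response evaluation".
- **Section 13.7.** It opens: "Each registered patient will be deemed as evaluable for toxicity, qualifying toxicities and response as per Section" 10.1. It then calls a best response of CR or PR a response, and defines non-responders as: "Best response assessment is stable disease or progressive disease or those patients who were not assessed or not evaluable". The study team does the coding, with the biostatistician's agreement.
- **Section 13.5.** "The overall best response rate to the drug combination will be estimated for the entire study population", and also for the PDGFRα-expressing cohort, with 95% confidence intervals. Evaluability is not mentioned.

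No section says which rule governs.

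**The concern.** Take a patient who stops treatment on day 20 and is never re-scanned. Under 3.3.2 and 10.1 this patient is not evaluable, is replaced, and drops out of the response rate. Under the 13.7 list the same patient is a non-responder, a label that has an effect only if the patient is in the denominator.

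The overall response rate, in all patients and in PDGFRα-positive patients, is a named secondary endpoint of a single-arm, open-label trial. Someone who leaves early or is never re-imaged cannot show a response confirmed at 4 weeks, so leaving such patients out moves the rate upward. With two rules on paper, the choice could be made after responses are known.

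**Working it through.** **1. The plan's own figure.** Section 13.2 states: "With a one-sided type I error of 5% and power of at least 80%, the first stage will enroll 16 response-evaluable patients". The trial continues with 4 or more successes in 16, adds 17 patients, and needs 11 or more of 33, with p0 = 0.2 and p1 = 0.4. The exact probability of success is the sum over x = 4 to 16 of P(Bin(16, p) = x) × P(Bin(17, p) ≥ 11 − x).

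- At p = 0.2: 0.0475, within 5%.
- At p = 0.4: 0.811, above 80%.
- Chance of stopping at stage 1 when p = 0.2: 0.598.

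The design reproduces. It runs on 6-month PFS, and 3.2, 13.2 and 13.4 all use response-evaluable patients for it, so the conflict does not reach it. It supplies the 33 used below.

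**2. Can the sections be reconciled?** Suppose 10.1 is applied first and 13.7 codes only those who pass.

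- Passing 10.1 requires disease re-evaluation, so nobody who passes is unassessed. That part of the 13.7 list would have no members.
- A patient who passes could still have an unclassifiable scan, so the non-evaluable part of the list could have members.

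Filtering first therefore explains half of the phrase and leaves the other half without meaning.

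**3. Is the group likely to be empty?** No section gives a non-evaluable share. Imaging is every 8 weeks (10.4), so a patient can complete 28 days and leave before any re-evaluation. Section 1.7 reports a cited study in which 5 of 10 sampled patients not on enzyme-inducing antiepileptics needed sorafenib interruption or modification in cycle 1. That is not a non-evaluable rate, but it makes zero an unsafe assumption.

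**4. Size of the gap.** Let d be the assumed non-evaluable share and x the number of responders, with no responder among the non-evaluable. The evaluable-only rate is x/33. The rate with everyone counted is x/N, where N = 33/(1 − d), rounded up. Take x = 4, which lies at the top of the 3-12% partial response range in Section 1.7. Intervals are Clopper-Pearson 95%.

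- Evaluable only: 4/33 = 12.1% (3.4 to 28.2).
- d = 10%: 33/0.9 = 36.7, so N = 37; 4/37 = 10.8% (3.0 to 25.4).
- d = 20%: 33/0.8 = 41.25, so N = 42; 4/42 = 9.5% (2.7 to 22.6).
- d = 30%: 33/0.7 = 47.1, so N = 48; 4/48 = 8.3% (2.3 to 20.0).

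The ratio of the two rates is N/33: 37/33 = 1.12, 42/33 = 1.27 and 48/33 = 1.45.

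For a group of 16 evaluable patients with 2 responders, 12.5% (1.6 to 38.3) becomes 2/18 = 11.1%, 2/20 = 10.0% or 2/23 = 8.7% at the same shares.

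**The case against.** The strongest reply is that the denominator is already fixed. Two objectives and two endpoints name response-evaluable patients, 10.1 replaces the others, and 7.8 takes them off study after the initial adverse-event follow-up. Section 13.7 refers back to 10.1 and names no denominator. On this view it holds one stray phrase in a coding list, which cannot override four explicit statements.

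Much of this stands, and it rules out several stronger readings that a reader might infer.

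- *That 13.7 codes every registered patient.* Its opening sentence assigns evaluability to registered patients under 10.1. It does not plainly say that all of them are coded.
- *That 13.5 adds a third denominator.* There the entire study population is set against the PDGFRα-expressing cohort, and 13.4 draws the same contrast while speaking of response-evaluable patients. It most naturally means molecularly unselected.
- *That the whole 13.7 category is empty under 3.3.2.* This is true of unassessed patients but not of patients with an unclassifiable scan.
- *That a few points of response rate decide the trial's outcome.* No decision rule uses the response rate. The 3-12% in Section 1.7 is background, and the denominators behind it are not given.

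What the reply cannot do is give meaning to the unassessed category once 10.1 has been applied. At least one section has to change, whichever denominator the sponsor intends.

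**Conclusion.** The point holds as a contradiction in how the secondary response-rate endpoints (3.3.2 and 3.3.3) are specified. It is worth correcting before responses are tabulated, but it is not a flaw in the primary analysis.

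Its size depends on a share that the documents do not give. Over an assumed 10% to 30%, a 12.1% rate falls by 1.3 to 3.8 percentage points, and the intervals overlap heavily. If every patient proves evaluable, the two rates coincide.

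The calculation also assumes no responders among the excluded. A strict reading of 10.1 would also exclude a patient whose sorafenib went below twice daily in the first 28 days. Such a patient could respond later, which would change the numerator as well.

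**What to change.** State one denominator in 3.3.2, 3.3.3, 13.5 and 13.7, and align 2.2.2 and 2.2.3 with it.

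- **Preferred rule:** all patients in the relevant cohort who started the three-drug combination on cycle 1 day 1. A best response of CR or PR counts as a response. Everyone else, including patients not assessed or not evaluable, is a non-responder, which keeps the coding already in 13.7.
- **Why cycle 1 day 1:** Section 6.2 allows valproic acid to be titrated before enrolment, so any exposure to a study drug would be an unclear starting point.
- **Supportive analysis:** the evaluable-only rate, with the number of patients excluded and the reasons.
- **Section 13.5:** say that the entire study population means patients unselected for PDGFRα, if that is what is meant.

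The replacement rule in 10.1 can stay for the 6-month PFS design. If the sponsor prefers the evaluable-only denominator, 13.7 should drop the unassessed category and say what non-evaluable means for a patient who has passed 10.1.

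The cost is wording only: no new data, visits or patients. The downside of the preferred rule is a slightly lower stated response rate.
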